1. SYNOPSIS

PROTOCOL: Clinical Investigation of the Bacterially-Derived Healon5 Ophthalmic Viscosurgical Device (OVD)
Protocol Number: VSCO-109-HLN5

STUDY TREATMENTS: Investigational Product: Bacterially-derived Healon5
Control Product: Currently-available, animal-derived Healon5

STUDY OBJECTIVE: The purpose of this clinical trial is to evaluate the safety and effectiveness of the bacterially-derived Healon5.

CLINICAL HYPOTHESIS: The bacterially-derived Healon5 OVD will be statistically non-inferior to the currently-available animal-derived Healon5 OVD with regard to cumulative intraoperative pressure (IOP) spikes and endothelial cell count (ECC) change at 3 months postoperatively.

OVERALL STUDY DESIGN:

Structure: Prospective, multicenter, paired-eye, randomized, masked, clinical trial of the bacterially-derived Healon5 OVD versus the currently available Healon5 OVD control.

Number of sites: Up to 10 sites in the USA

Duration: 3 months

Administration: Surgeons will use the OVD as they normally would to perform standard, small-incision, cataract surgery and implant subjects with one of the following intraocular lenses (IOLs): TECNIS[®] ZCB00 monofocal IOL, TECNIS[®] Multifocal IOLs (ZKB00, ZLB00, or ZMB00) or the TECNIS[®] Symphony Extended Range of Vision IOL (ZXR00).

Visit Schedule: All subjects will undergo a minimum of 11 visits:
Preoperative for both eyes; 1st eye operative;
Postoperative for 1st eye at 6 hours, 1 day and 1 week; 2nd eye operative; Postoperative for 2nd eye at 6 hours, 1 day and 1 week; 1 month and 3 months postoperative for both eyes together.

STUDY POPULATION CHARACTERISTICS:

Condition: Bilateral cataracts with otherwise healthy eyes

Number of Subjects: Up to 241 subjects will be enrolled to ensure treatment of approximately 230 subjects in order to achieve approximately 200 evaluable subjects at 3 months

Each site should enroll approximately 20 subjects, and no site may enroll more than 25% (60 subjects) of the enrollment total.

Inclusion Criteria (all criteria apply to each study eye):

- Minimum 22 years of age
- Cataracts for which extraction and posterior IOL implantation have been planned for both eyes
- Potential for postoperative best corrected distance visual acuity (BCDVA) of 20/40 Snellen or better
- Clear intraocular media, other than cataract
- Availability, willingness and sufficient cognitive awareness to comply with examination procedures
- Signed informed consent and HIPAA authorization

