Inclusion and exclusion qualifications will be assessed at the preoperative visit according to the inclusion/exclusion criteria. The Informed Consent Document and Authorization for Use/Disclosure of Health Information form (HIPAA authorization) must be signed by

any patients who agree to participate in the study prior to undergoing any study-specific procedures. After determination that all inclusion/exclusion criteria have been met, enrolled subjects will be randomized in a 1:1 ratio. Subjects will receive the study OVD in one eye and the currently-available control OVD in the fellow eye. Subjects and study personnel will be masked for the duration of the study.

Key preoperative data include ocular health and history, visual acuities, manifest refraction, IOP, ECC, biomicroscopic slit-lamp findings, ocular symptoms and biometry. The operative visit will include standard procedures for cataract surgery and IOL implantation. All aspects of laser cataract surgery will be allowed as well as astigmatic keratotomy (AK) and Limbal Relaxing Incisions (LRI). If laser cataract surgery, AK or LRI is elected, it must be performed on both eyes of the subject.

A standardized medication regimen will be used preoperatively and intraoperatively (Section 10.5, Medication Regimen). Key postoperative data collection includes IOP, ECC, manifest refraction, visual acuity, visual symptoms, biomicroscopic slit-lamp findings, and adverse events.

As this study is masked, an independent Data Safety Monitoring Board (DSMB) will monitor adverse events that occur during the study.

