10.4 RANDOMIZATION AND MASKING

A randomization list will be created by the AMO biostatistician for each investigative site. Subjects will be randomly assigned to receive either the bacterially-derived Healon5 or the animal-derived Healon5 control in the first operative eye on a 1:1 basis; subjects will then receive the OVD not used in the first-eye surgery in the fellow eye. The randomization codes will be uploaded into the electronic data capture system (EDC). Study personnel at the site will be trained in the randomization process through the EDC system and will randomize subjects as they are enrolled. Randomization will take place after the subject has signed the informed consent document, has met all inclusion and exclusion criteria, and the investigator has documented which eye will be the first to undergo surgery.

As part of the informed consent process, the investigator or delegate will explain to the subject the requirements of a randomized, masked study and the differences between the two OVDs.

In order to ensure masking of all study personnel, both the investigational and control OVDs will be packaged the same in white boxes labeled "Investigational Device".

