10.8 EXIT OF SUBJECTS

An Exit Case Report Form will be submitted for all subjects, either when they complete the study or if they exit early.

It is the responsibility of the investigator to provide complete follow-up data to AMO for each subject, and every attempt should be made to gather that complete follow-up data for all subjects enrolled as missing data can have a negative effect on the study results. Patients who would be traveling, relocating or otherwise unavailable for postoperative follow-up visits should not be chosen for this clinical study.

If a subject dies prior to study completion, he/she will be documented as discontinued from the study along with the reason for death. Subjects will be considered “lost-to-follow-up” from the study only if irretrievably lost for unavoidable reasons such as: subject moved/unable to locate, subject uncooperative/refuses further study participation, subject ill/unable to travel. In the event of subject relocation, efforts must be made by the investigator to secure follow-up information (i.e., IOP, slit-lamp findings and general visual acuity, etc.) from the subject’s new physician.

A subject will be considered a non-randomized screen failure if he/she does not meet the inclusion/exclusion criteria or if consent is withdrawn prior to randomization.

A subject will be considered a randomized screen failure if the subject is randomized but does not undergo surgery or receive one of the study OVDs for various reasons including: the surgery being aborted, the subject withdrawing consent prior to treatment or the subject dying prior to treatment. If a subject receives the study OVDs in either eye, he/she is to be followed according to the protocol.

If a subject is exited early from the study, the investigator will submit an Exit Case Report Form indicating the reason for study exit. In the event of a serious adverse event, the subject may be exited from the study; however, efforts must be made by the investigator to follow the subject until resolution of the adverse event.

Following study completion or early exit, subjects will be informed about which OVD was used in each eye. Additionally, all study subjects are to be instructed to undergo regular eye examinations at least yearly and to return to their doctor if any eye complications are experienced in the interim.

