15.1 DATA MONITORING

In order to ensure a well-controlled clinical trial, AMO will follow specific data monitoring procedures. As this study is masked, any necessary review of safety and effectiveness data by OVD type will be done only by the Data Safety Monitoring Board (Section 15.3) until the final study visits are completed. Study staff and AMO personnel will remain masked until the final study visits have been completed.

An electronic data capture system (EDC) will be used to transmit case report forms from the investigative site to AMO. Requests for data clarification will be handled through this same system.

To minimize data omissions and inconsistencies on clinical reports and to ensure that data are accurately transcribed to computer data files, AMO will follow internal data processing procedures that include automated and manual quality control checks to identify any data discrepancies. Any such items will be resolved and documented as needed on the case report forms at the investigative site and in the data management system at AMO.

Prevention of Missing Data

Methods used to safeguard against missing data that can have deleterious effects on the study integrity and reliability of its outcomes will include training study staff with WebEx and on-site programs. In addition, subjects will be encouraged at the time of informed consent to avoid missing study visits, as missing data may affect the study reliability and diminish the scientific value of their contribution to the study.

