15.3 SAFETY MONITORING

This study will use a Data Safety Monitoring Board (DSMB) for safety monitoring. In alignment with ISO 14155:2011(E), the DSMB is an independent committee that is established by AMO to assess, at intervals, the progress of the clinical investigation, the safety data, or the critical performance endpoints, and to recommend to the sponsor whether to continue, suspend, or stop the clinical investigation. The DSMB will have access to the randomization code to be able to assess safety by OVD group if required. The responsibilities of the DSMB will be detailed in a separate written procedure to establish the frequency of meetings, handling of emergency situations and documentation of such meetings.

This study will also utilize a Medical Monitor for safety monitoring. The Medical Monitor will remain masked until the final study visits have been completed. The Medical

Monitor will review and assess any reports of serious and/or device-related adverse events as well as device deficiencies that could have led to a serious adverse event. If necessary, the medical monitor will discuss these events with the reporting investigator(s), without being specific about OVD type. If unmasking is required by the Medical Monitor to protect the safety of the subject(s), a request will be submitted and approved by Head of Clinical Research and Head of Biostatistics prior to release of the randomization code for only the subject(s) involved, and the IRB will be notified. The medical monitor will also be available to answer all questions from investigators. The medical monitor, as well as any other qualified personnel designated by AMO, shall also review interim progress reports, as applicable.

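### Section 10.8 has subjects told their OVD assignment after completion or early exit, with no deferral to the end of the trial, and this is not reconciled with the study's masking rules

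*Protocol*

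**What the plan says.** Protocol Section 10.8 contains the disclosure rule: "Following study completion or early exit, subjects will be informed about which OVD was used in each eye". It gives no earliest date, names nobody to do the informing, and does not say how the code is obtained. Earlier in the same section an exit form is due for every subject "either when they complete the study or if they exit early", so the section treats completion as something each subject reaches individually.

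The masking rules are elsewhere in the protocol:

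- Synopsis: "Subjects and study personnel will be masked for the duration of the study".
- Section 15.1: "Study staff and AMO personnel will remain masked until the final study visits have been completed".
- Section 15.3: if the Medical Monitor needs unmasking for safety reasons, two sponsor function heads must approve "prior to release of the randomization code for only the subject(s) involved, and the IRB will be notified".

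Site contact can continue after exit. For a subject exited because of a serious adverse event, Section 10.8 says "efforts must be made by the investigator to follow the subject until resolution of the adverse event". Section 11.5 extends follow-up to those exited for device-related events.

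The SAP does not address when subjects are unmasked.

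**The concern.** A site that follows Section 10.8 as written would naturally tell a subject the assignment when that subject leaves or finishes. The site is the subject's point of contact, so its staff may learn the code by delivering it, or may hear it from the subject later. Sections 10.8 and 15.1 could then not both be honoured.

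At stake are the judgments made at the site. IOP is read by Goldmann applanation against a 30 mmHg threshold and feeds a primary endpoint. Slit-lamp grades feed a secondary safety endpoint. The relation of an event to the device is judged under Section 11.4. Section 10.7 recommends that one person do all postoperative testing at a site, with the slit-lamp exam left to the investigator or a qualified designee. An unmasked assessor may therefore be the person examining the subjects who remain.

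**Working it through.** The point rests on no alpha, power or sample size, so there is no stated figure to reproduce. The check compares the texts and adds a few short sums for timing and scale.

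**1. When can disclosure fall?**
- Early exit comes before the subject's own 3-month visit. If disclosure is made at exit, other subjects are normally still in follow-up.
- For completers, Section 10.2 puts second-eye surgery 14 to 45 days after the first, and the 3-month visit 75 to 105 days after the second. A subject therefore finishes between 14 + 75 = 89 and 45 + 105 = 150 days after first-eye surgery. Section 8 has sites enrolling sequentially, so finishing dates are spread out, and most subjects finish before the last subject's final visit.
- The enrolment period is not given. The documents do not show how many subjects would still be unrandomized at any disclosure.

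**2. Do the masking rules allow this?**
- The Synopsis could be read per subject, so that an exited subject's own masking has ended. It also covers personnel, whose masking does not end with one subject.
- Section 15.1 refers to final visits in the plural and ties the rule to review of data by OVD type. Both point to study-wide visits.
- Section 15.3 puts two approvals and an IRB notice around release of one subject's code to the Medical Monitor. Section 10.8 puts no approval, record or containment around routine disclosure.
- No passage reconciles these rules.

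**3. Who becomes unmasked?** As written, only the subject. Staff become unmasked if they deliver the code, see it, or are told it by the subject. The last of these is most plausible when follow-up continues after exit.

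**4. What is exposed?**
- IOP, slit-lamp grades and causality calls are produced at the site.
- ECC is not exposed in the same way. Appendix C sends the images to a central reading center without the treatment group.

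**5. Scale.** The Synopsis enrolls enough "to ensure treatment of approximately 230 subjects in order to achieve approximately 200 evaluable subjects at 3 months".
- Treated but not evaluable: 230 − 200 = 30.
- Share of treated: 30 / 230 = 13.0%.
- Per site, if all 10 sites open: 30 / 10 = 3.

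These are rough ceilings on treated early exits, because some of the 30 may simply have missing data without leaving. If completion is per subject, the sentence also covers the roughly 200 who finish.

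**The case against.** The strongest reply is that Section 10.8 sets a sequence and not a date. Informing every subject once the last visits are done would satisfy Sections 10.8 and 15.1 and the Synopsis together. This stands in part: the text permits a compliant reading, so mid-trial disclosure is an inference. But the sentence does not require the delay, and the section's own per-subject use of completion points the other way.

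A reader might infer three stronger claims that the documents do not support.

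- **That the site must learn the code.** Section 10.8 is in the passive voice and gives sites no route to the code. Both OVDs come in identical packaging (Section 10.4), and the sponsor could inform subjects directly. Staff unmasking is likely, but it is not written.
- **That one disclosure reveals other subjects' assignments.** Section 10.4 says only: "A randomization list will be created by the AMO biostatistician for each investigative site". Neither document mentions blocks. With an assumed block of 2, one known assignment fixes its partner. With an assumed block of 4, two of the three remaining places carry the opposite assignment (2/3 = 67%). Both figures also require staff to know which subjects share a block. Without blocking, one subject's code says nothing about the next subject's.
- **That 13% of treated subjects will be told early.** The 30 is an allowance for non-evaluability. It can include missed visits, deaths and subjects who cannot be located, and the last two groups could hardly be informed.

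The effect on endpoints is also limited. Exited subjects contribute little later data, and ECC is read masked. Serious events are reported within 48 hours and reviewed by a masked Medical Monitor, so many causality judgments would come before any disclosure. All of this lowers the size of the problem without removing the inconsistency.

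**Conclusion.** The point holds as an unreconciled inconsistency with a modest practical risk. On its ordinary reading Section 10.8 lets assignments be disclosed while the study is still being assessed. That undercuts the masking in the Synopsis and Section 15.1 and goes around the control in Section 15.3.

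The most direct exposure is an exited subject whose adverse event is still being followed and attributed by the investigator. Effects on other subjects' IOP readings and slit-lamp grades, or on the choice of first eye, would require staff to learn the code and then be able to infer further assignments. The inference depends on blocking, which is not stated.

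The conclusion assumes that completion is per subject, as Section 10.8 uses it elsewhere, and that Section 15.1 means the study's last visits. No bias can be quantified from the documents; 30 of 230 (13%) bounds treated early exits only roughly.

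**What to change.** Amend Section 10.8 so that all subjects, including those who exit early, are told which OVD each eye received only after the last subject's final study visit. State who tells them. Allow earlier release only through the safety route in Section 15.3.

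The last subject's final visit matches the point at which Section 15.1 ends staff masking. Waiting for database lock would go further than the protocol's own rule and is not needed to remove the inconsistency.

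Align the consent text if it promises earlier disclosure; the consent pages were not available to check. The change is one or two sentences. The downside is that subjects who exit or finish early wait longer for the information.

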10.9 UNSCHEDULED VISITS

During the study period, if a non-protocol-required visit is done for the purpose of medically-indicated follow-up for either study eye, data from this visit should be submitted using the Unscheduled Visit CRF. The need for unscheduled visits is at the investigator's discretion. Specific examinations to be performed at unscheduled visits are also at the discretion of the investigator (based on the reason for the unscheduled visit), and data are to be recorded in the appropriate section of the case report form.

Data to be collected may include:

- Uncorrected and best corrected distance visual acuity
- Intraocular pressure
- Slit-lamp examination for medical and/or lens findings
- Dilated fundus exam
- Ocular symptoms
- Adverse events
- Medications

10.10 PROTOCOL DEVIATIONS

Any departure from the protocol procedures represents a protocol deviation. Protocol deviations may be subject-based (e.g., inclusion/exclusion criteria, informed consent deviation, etc.) or procedural-based (e.g., out-of-interval visits, non-compliance with testing procedures, etc.). All protocol deviations will be documented using protocol deviation case report forms. Any deviation made to protect the life or physical well-being of a subject in an emergency, as well as any use of the investigational device without obtaining informed consent, must be reported to AMO within 5 working days. Protocol deviations will be monitored by AMO, and if the non-compliance is persistent or egregious, AMO may take action, including but not limited to termination of the investigator's participation in the study. The investigator is also responsible for informing the reviewing IRB of instances of protocol non-compliance in accordance with the IRB requirements.

11. ADVERSE EVENTS AND PRODUCT COMPLAINTS

11.1 ADVERSE EVENT DEFINITIONS

Adverse Event (AE)

An adverse event is defined (following ISO 14155) as any untoward medical occurrence, unintended disease or injury, or untoward clinical signs (including abnormal laboratory findings) in subjects, users or other persons, whether or not related to the study device.

Serious Adverse Event (SAE)

An adverse event is considered serious (following ISO 14155) if it is an untoward occurrence which may or may not be related to use of the study device that

- is sight- or life-threatening,
- results in death,
- requires inpatient hospitalization or prolongation of hospitalization (a planned hospitalization for a pre-existing condition without a serious deterioration in health is not considered a serious adverse event),
- results in permanent impairment of a body structure or body function,
- necessitates medical or surgical intervention to prevent permanent impairment to a body structure or function, or
- results in fetal distress, fetal death or a congenital abnormality or birth defect

Device-Related Adverse Event/Adverse Device Effect (ADE)

A device-related adverse event is defined as any adverse event that is believed to be definitely, probably or possibly related to the study device (following the guidelines in Section 11.4, Causal Relationship). A device-related event is also considered an adverse device effect (ADE; following ISO 14155) resulting from the use of the study device that may result from user error, insufficiencies or inadequacies in the instructions for use, deployment, implantation, installation, operation or any malfunction of the device.

Study-Specific Serious Anticipated Adverse Events

The following is a list including, but not limited to, ocular adverse events that are anticipated and must be reported to AMO for this study. Any events that are unlikely but anticipated (i.e., endophthalmitis) will be reported to the FDA.

- Endophthalmitis/Intraocular infection
- Hypopyon
- Hyphema
- IOL dislocation
- IOP 30 mmHg or greater at any time or persistent IOP of any level requiring treatment
- Cystoid macular edema
- Pupillary block
- Retinal detachment/tear
- Persistent corneal edema
- Persistent iritis
- Visual symptoms requiring secondary surgical intervention (e.g., lens removal)
- Tilt and decentration requiring secondary surgical intervention (e.g., repositioning)
- Residual refractive error resulting in a secondary surgical intervention
- Retained lens material resulting in secondary surgical intervention

NOTE 1: Suture removal, planned blepharoplasty and Nd:YAG capsulotomy (for PCO) are not considered adverse events for this study.

NOTE 2: Corneal edema and iritis will be reported as serious adverse events if sight-threatening at any time or persistent at the final study visit (75-105 days postoperative). Treatment merely to hasten the resolution of such conditions (and not intended to prevent permanent damage to the eye) will not be reported as serious adverse events.

Unanticipated Adverse Device Effect (UADE)/Unanticipated Serious Adverse Device Effect (USADE)

Any UADE (USA 21CFR 812.3(s)) or USADE (ISO 14155) is defined as any serious adverse effect on health or safety or any life-threatening problem or death caused by, or associated with, a device, if that effect, problem, or death was not previously identified in nature, severity, or degree of incidence in the investigational plan (i.e., this protocol), application (including a supplementary plan or application), or risk assessment, or any other unanticipated serious problem associated with a device that relates to the rights, safety, or welfare of subjects.

